### **7.1.3. Expansion cohort**

Once the MTD is established, an expansion cohort will further evaluate safety, clinical and immune responses, to give a total of 21 patients at the MTD of MV-NIS in combination with standard-dose atezolizumab: MV-NIS at the established MTD given by intra-tumoral injection on day 1 followed by atezolizumab at 1200 mg IV on day 15 and subsequently every 3 weeks.

### **7.1.4. Viral and safety monitoring**

In both the escalation and expansion cohorts, the *in vivo* distribution of MV-NIS infected cells and the kinetics of virus spread and elimination will be monitored by SPECT/CT imaging.

Technetium-99m (99mTc) SPECT/CT imaging will be performed prior to registration, 7 days after MV- NIS administration and 15 days after MV-NIS administration if previous scan is positive.

A safety committee will be established to monitor and evaluate the safety of patients and to maintain oversight of study data and monitoring process. The board will consist of the Vyriad study team, the investigators and any other person the investigators consider necessary to assist with study decisions. The board will meet according to the Safety Committee Charter established at the beginning of the trial. The safety committee will also meet at unscheduled times according to clinical necessity. All SAEs will be reported to the safety committee within 3 working days after learning of the event.

If a suspected DLT occurs, a safety committee meeting will be held as rapidly as possible. In the meantime, dosing of the ongoing patients in that cohort will continue unless there is reason to suspect there is an unacceptable safety risk based on the nature and/or severity of the observed DLT.

The decision to dose escalate will be made collectively by the safety committee. Dose Escalation Teleconferences (DETs) will occur prior to dose escalation for subsequent cohorts. The cumulative safety experience, which includes data from the current and previous dose cohorts, will be discussed by the Sponsor and the Investigators.

Based on the data presented and ensuing discussion during the teleconference, decisions such as implementation of additional monitoring, continuation of enrollment, or dose adjustments will be made by those present. Minutes from each meeting will be taken and formal notification of recommendations and decisions will be communicated to all study sites by the Sponsor or designee after the meeting.

Should a patient develop measles, treatment with immune globulin will be administered 400 mg/kg/d for 3-5 days. Aerosolized Ribavirin (6 grams/day over 12-18 hours/day for 3 days, up to 7 days in length) can also be considered at the discretion of the treating physician for patients not responding to immune globulin.

The National Cancer Institute Common Terminology Criteria for Adverse Events (NCI CTCAE; Version 4.03) will be used for grading toxicities. Safety assessments will include adverse events (AEs), serious adverse events (SAEs), vital sign measurements, ECOG status, clinical safety laboratory evaluations (hematology, serum chemistry, coagulation and urinalysis). In the case of grade 3-4 laboratory abnormalities, and any other clinically significant lab findings which potentially meet the definition of DLT, repeat tests must be performed every 1-2 days in order to verify duration accurately and observe recovery.

### **7.1.5. Efficacy and pharmacodynamics**

Patients will be evaluated for efficacy (tumor response) according to RECIST 1.1 and irRECIST criteria.

PD assessments will include RT-PCR of MV-NIS. Mouth swabs and urine samples will also be collected for evaluation of viremia. Correlative blood sampling for biomarkers of immune response will be collected at key time points during the study. Pre and post (if feasible) treatment tumor tissue biopsies will be used for correlative research. Blood sampling for flow cytometry or functional immune cell analysis will be used to analyze peripheral blood immunocyte populations and to collect information on free DNA to measure change in tumor

levels in the blood.

## 7.2. Discussion of Study Design

An open-label single ascending dose escalation design is the standard design to define the safety, tolerability, and MTD of MV-NIS.

## 7.3. Conditions for Terminating the Study

Vyriad has the right to terminate the study at any time. In terminating the study, Vyriad and the investigator will ensure that adequate consideration is given to the protection of the patients' interests. Reasons for study discontinuation may include, but are not limited to the following:

- The incidence or severity of AEs in this or other studies evaluating MV-NIS indicates a potential health hazard to patients.
- Patient enrollment is unsatisfactory.
- Drug supply issues.
- Data recording is inaccurate or incomplete.
- Excessive patient self-withdrawal.
- Significant protocol deviations (e.g., violation of eligibility criteria, dosing errors, missing data for study endpoint analysis).

The following data and materials are required by Vyriad before a study can be considered to be complete or terminated:

- Laboratory findings, clinical data, and all special test results from screening through the end of the study, including the follow-up period for all enrolled patients.
- Case Report Forms/Records. Electronic case report forms (eCRFs) will be used in this study. Records (including correction forms) for all enrolled patients will be properly completed by appropriate study personnel, and signed and dated by the principal investigator, as required.
- Principal investigator sign-off of all required CRF forms.
- Completed Drug Accountability Records, Drug Inventory Log, and Inventory of Returned Drug forms or documentation of destruction, as appropriate.
- Return of all unused study drug to Vyriad unless an alternate disposition method is agreed upon at study initiation by Vyriad and investigational site(s).
- Copies of protocol amendments and other documents, and IRB approval/notification, as applicable.
- A summary of the study prepared by the principal investigator (IRB summary closure letter is an acceptable equivalent).

## 8. STUDY POPULATION

### 8.1. Target Population

This study will be conducted in up to 24 patients with metastatic lung cancer, with histologic confirmation of the primary NSCLC histology and with at least one lesion amenable for intra-tumoral injection with MV-NIS.

Note: all eligibility criteria must be verified and submitted to the medical monitor to permit study registration. Day 1 may only occur after registration (at least 1 day and up to 7 days later).

### 8.2. Inclusion Criteria

Patients will be included if they meet the following criteria:

1. Age  $\geq$  18 years.
2. Diagnosis of metastatic lung cancer, with:
  - a. Histologic confirmation of the primary NSCLC histology
  - b. At least one lesion amenable for intra-tumoral injection of MV-NIS.
3. Patient meets the FDA-approved indication for atezolizumab treatment in NSCLC ([Tecentriq® USPI 2016](#)).
4. Patient may have more than one site of recurrence/metastatic disease but only one lesion will be injected that is  $\geq$  1 cm in size (if in the lung, the lesion must be  $\geq$  2 cm and adjacent to the pleura).
5. Measurable disease per RECIST 1.1.
6. ECOG Performance Status (PS) 0 or 1.
7. Ability to provide informed consent.
8. Willingness to comply with all required protocol procedures including providing biologic specimens, participating in the SPECT/CT imaging and returning to the clinical study site for follow up visits.
9. Life expectancy of more than 12 weeks (in the opinion of the enrolling investigator).
10. The following laboratory values obtained  $\leq$  14 days prior to registration.
  - a. ANC  $\geq$  1500/mm^3
  - b. Platelets  $\geq$  100,000/mm^3
  - c. HgB  $>9.0$  g/dL
  - d. Total bilirubin  $\leq$  institutional upper limit of normal (ULN)
  - e. SGOT (AST)  $\leq$  2.5 x ULN
  - f. Creatinine  $\leq$  1.5 x ULN
11. Must be willing to implement contraception throughout study and for the 8 weeks following last study drug administration.

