Hematologic:	$\geq$ grade 3 as per NCI Common Terminology Criteria for Adverse Events (CTCAE) v4.03 except grade 3 ANC lasting $<72$ hours.												
Renal:	Serum creatinine $\geq 2$ times baseline.												
Viremia:	Lasting for $\geq 4$ weeks after intratumoral injection.												
Clinical measles:	Any grade per CDC definition ( http://www.cdc.gov/measles/hcp/index.html )												
Other non-hematologic, including:	$\geq$ grade 3 AE as per NCI CTCAE v4.03.												

 
• Allergic reactions
 
• Autoimmune toxicity
 
• Organ toxicity
 
													

	
The AE reporting period for a patient enrolled in the study begins when the patient provides informed consent and is continued through 30 days after the last dose of study drug (MV-NIS or atezolizumab). All AEs that occur in enrolled patients during screening and study drug treatment must be recorded in the case report forms (CRFs), regardless of the relationship of the AE to study drug. All SAEs occurring between informed consent and through the 30-day follow-up period after last study drug administration should be reported to Vyriad regardless of relationship to study drug. All related AEs ongoing at discontinuation of study drug should be reported until resolution or stabilization. Any known untoward event that occurs beyond the AE reporting period that the investigator assesses as possibly related to MV-NIS should also be reported to Vyriad.
 
Vital sign measurements, including sitting blood pressure, pulse rate, respiratory rate, and temperature will be monitored throughout the study.

PK evaluation	
The in vivo distribution of MV-NIS infected cells and the kinetics of virus spread and elimination will be monitored by SPECT/CT imaging.
 
SPECT/CT imaging will be performed prior to registration, 7 days after MV-NIS administration and 15 days after MV-NIS administration if previous scan is positive.

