**Table 3: MV-NIS Dose Levels**

Dose Level	Number of viruses
-1	$3 \times 10^7$
1	$1 \times 10^8$
2	$3 \times 10^8$
3	$1 \times 10^9$

Atezolizumab will be given per the US prescribing information ([Tecentriq® USPI 2016](#)) at 1200 mg IV on day 15 and then every 3 weeks thereafter until progression of disease, discontinuation due to toxicity, or withdrawal of consent.

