### 8.3. Exclusion Criteria

Patients who meet any of the following criteria will be excluded from study entry:

1. Patients with any other prior malignancy are not allowed except for the following:
  - a. Adequately treated basal cell or squamous cell skin cancer
  - b. In situ cervical cancer
  - c. Adequately treated Stage I or II cancer from which the patient is currently in complete remission or other cancer from which the patient has been disease-free for 2 years.
2. Uncontrolled CNS metastases or treatment by neurosurgical resection, radiation or brain biopsy within 4 weeks prior to Day 1.
3. Prior treatment with an anti-PD-1, anti-PD-L1, anti-PD-L2, anti-CTLA-4 antibody, or any other antibody or drug specifically targeting T-cell co-stimulation or immune checkpoint pathways.
4. Any of the following prior therapies:
  - a. Chemotherapy  $\leq$  3 weeks prior to registration;
  - b. Biologic therapy  $\leq$  4 weeks prior to registration;
  - c. Radiation therapy  $\leq$  3 weeks prior to registration;
  - d. Investigational therapy  $\leq$  4 weeks prior to registration.
5. Failure to fully recover from acute, reversible effects defined as  $\leq$  grade 1 CTCAE v.4.03 of prior systemic therapy regardless of interval since last treatment.
6. Other concurrent investigational therapy (utilized for a non-FDA-approved indication and in the context of a research investigation).
7. Any of the following because this study involves an agent that has known genotoxic, mutagenic and teratogenic effects:
  - a. Pregnant women
  - b. Nursing women
  - c. Men or women of childbearing potential who are unwilling to employ adequate contraception during treatment and 8 weeks following the completion of study drug treatment.
8. Patients with active, known or suspected autoimmune disease. Exceptions are vitiligo, type I diabetes mellitus, residual hypothyroidism due to autoimmune condition only requiring hormone replacement, psoriasis not requiring systemic treatment, or conditions not expected to recur in the absence of an external trigger.
9. Patients with a condition requiring systemic treatment with either corticosteroids ( $> 10$  mg daily prednisone equivalent) or other immuno-suppressive medications within 14 days of study drug administration. Inhaled or topical steroids, and adrenal replacement doses  $> 10$  mg daily prednisone equivalents are permitted in the absence of active autoimmune disease.
10. History of organ transplantation.

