### **5.8 Embryo-Fetal Toxicity**

Based on its mechanism of action, TECENTRIQ can cause fetal harm when administered to a pregnant woman. Animal studies have demonstrated that inhibition of the PD-L1/PD-1 pathway can lead to increased risk of immune-related rejection of the developing fetus resulting in fetal death. If this drug is used during pregnancy, or if the patient becomes pregnant while taking this drug, advise the patient of the potential risk to a fetus. Advise females of reproductive potential to use effective contraception during treatment with TECENTRIQ and for at least 5 months after the last dose [*see Use in Specific Populations (8.1, 8.3)*].

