### **8.3 Females and Males of Reproductive Potential**

#### **Contraception**

##### ***Females***

Based on its mechanism of action, TECENTRIQ can cause fetal harm when administered to a pregnant woman [*see Use in Specific Populations (8.1)*]. Advise females of reproductive potential to use effective contraception during treatment with TECENTRIQ and for at least 5 months following the last dose.

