#### Embryo-Fetal Toxicity

Advise female patients that TECENTRIQ can cause fetal harm. Instruct females of reproductive potential to use effective contraception during treatment and for at least 5 months after the last dose of TECENTRIQ [*see Use in Specific Populations (8.1, 8.3)*].

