**Before you receive TECENTRIQ, tell your healthcare provider about all of your medical conditions, including if you:**

- have immune system problems such as Crohn's disease, ulcerative colitis, or lupus
- have had an organ transplant
- have lung or breathing problems
- have liver problems
- have a condition that affects your nervous system, such as myasthenia gravis or Guillain-Barré syndrome
- are being treated for an infection
- are pregnant or plan to become pregnant. TECENTRIQ can harm your unborn baby. If you are able to become pregnant, you should use an effective method of birth control during your treatment and for at least 5 months after the last dose of TECENTRIQ.
- are breastfeeding or plan to breastfeed. It is not known if TECENTRIQ passes into your breastmilk. Do not breastfeed during treatment and for at least 5 months after the last dose of TECENTRIQ.

**Tell your healthcare provider about all the medicines you take,** including prescription and over-the-counter medicines, vitamins, and herbal supplements.

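### For women of childbearing potential, the entry criteria require contraception for 8 weeks after the last study drug, about 3 months less than the 5-month minimum in the appended atezolizumab label

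*Combined protocol and SAP*

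**What the plan says.** Two eligibility criteria set the contraception period, and the Synopsis repeats both.

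- Section 8.2, inclusion 11, applies to all patients: "Must be willing to implement contraception throughout study and for the 8 weeks following last study drug administration".
- Section 8.3, exclusion 7c, bars men or women of childbearing potential who are "unwilling to employ adequate contraception during treatment and 8 weeks following the completion of study drug treatment".

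Both agents count as study drug: the safety paragraph of the Synopsis runs the adverse-event window to "30 days after the last dose of study drug (MV-NIS or atezolizumab"). MV-NIS is injected once, on Day 1. Atezolizumab is given at "1200 mg IV on day 15 and then every 3 weeks thereafter until progression of disease" (Section 7.1.1), or until toxicity or withdrawal of consent.

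Appendix 2 reproduces the October 2016 atezolizumab label, which gives a longer period for females in four places:

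- Section 8.3 of the label: "use effective contraception during treatment with TECENTRIQ and for at least 5 months following the last dose".
- Section 5.8 gives the same minimum and the reason for it: "TECENTRIQ can cause fetal harm when administered to a pregnant woman".
- Section 17, patient counselling: "use effective contraception during treatment and for at least 5 months after the last dose of TECENTRIQ".
- The Medication Guide: "use an effective method of birth control during your treatment and for at least 5 months after the last dose of TECENTRIQ".

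The label gives no contraception period for men.

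**The concern.** The protocol sets its own contraception period, and that period is shorter than the one in the label of the drug most patients will receive last. It gives no reason for 8 weeks after atezolizumab. Exclusion 7 justifies itself by genotoxic, mutagenic and teratogenic effects, so protecting a fetus is plainly part of its purpose.

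Fetal exposure is what is at stake. A woman of childbearing potential who will commit to 8 weeks and no more is eligible as the criteria stand. After entry, contraception is the main preventive measure: Table 1 schedules a pregnancy test at screening only, and Section 11.4.12 deals with reporting and following pregnancies, not preventing them.

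**Working it through.** The plan gives no derivation of the 8 weeks, so there is no figure to reproduce. The check compares the stated periods and asks whether other text lengthens the shorter one.

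**1. When the clock starts.** MV-NIS is given once, on Day 1, and atezolizumab from Day 15 every 3 weeks. For any woman who reaches Day 15, the last study drug is normally atezolizumab, so both periods count from the same dose.

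**2. Whether the rest of inclusion 11 lengthens the period.** It also covers the time on study.

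- Stopping for progression: the Synopsis (duration of participation) and Section 12.1.22 put the last mandatory visit about 30 days after the last dose. The binding limit is max(30, 56) = 56 days.
- Stopping without progression: follow-up continues until progression (Section 9.3.2), so inclusion 11 can run past 56 days. Exclusion 7c still counts 8 weeks from the end of treatment.

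**3. The gap.**

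- Protocol: 8 × 7 = 56 days.
- Label: 5 months = 150 days with 30-day months, up to 153 by the calendar.
- Shortfall: 150 − 56 = 94 days, or 153 − 56 = 97 days, about 3 months.
- Ratio: 56/150 = 37.3%; 56/153 = 36.6%.

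**4. What this means by case.**

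| Case | Current text | Label period added |
|---|---|---|
| One atezolizumab dose on Day 15, stopped for progression | 15 + 56 = Day 71 | 15 + 150 = Day 165, to 15 + 153 = Day 168 |
| MV-NIS only, on Day 1 | at least 1 + 56 = Day 57 | at least Day 57 (label period does not apply) |

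The second case is possible because a patient with a DLT is taken off study drugs (Section 7.1.2) and a patient with measles is removed from the trial (Section 9.1.8.2). Either can happen before Day 15.

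**5. Drug exposure, for context only.** Label Section 12.3 gives a terminal half-life of 27 days.

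- 8 weeks: 56/27 = 2.1 half-lives. Under simple exponential decline, 0.5^2.1 leaves about 24% of drug.
- 5 months: 150/27 = 5.6 half-lives, leaving about 2%.

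No document gives an exposure threshold for fetal harm, so this is not a risk estimate.

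**6. How many women.**

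- Enrolment from Section 7.1: 9 + 15 = 24 to 24 + 18 = 42.
- Share of women: label Section 14.2 reports 61% and 59% men in its two NSCLC trials, so 39% to 41% women.
- Women enrolled: 24 × 0.39 = 9.4 to 42 × 0.41 = 17.2.
- Of childbearing potential: not given. The median ages in those trials were 64 and 62, so the share should be low. With an assumed 2% to 10%: 9.4 × 0.02 = 0.2 to 17.2 × 0.10 = 1.7, that is 0 to 2 women.

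The enrolment range is not firm. Section 8.1 speaks of up to 24 patients in all, and re-enrolling the expansion cohort at a lower dose (Section 7.1.2) could take the total above 42. The number affected stays small either way.

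**The case against.** The strongest reply is that the 5-month advice is already in the protocol. The whole label is appended, including its counselling section and Medication Guide, and atezolizumab is to be given according to it. The label advises and the criterion sets a minimum for entry, so the two do not contradict each other: a site can enrol at 8 weeks and still counsel 5 months. What a woman is told is settled mainly at consent, and that text was not available. At most a couple of women are involved, perhaps none.

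Much of this stands. The finding cannot say that any woman would be misinformed, and the numbers are small. It does not remove the defect, though. The protocol body invokes the label for indication, dosing, and dose modifications or delays. On contraception it states its own, shorter period, and a general reference to the label for dosing cannot be taken to override an explicit criterion. If the consent form already says 5 months, the criteria should agree with it.

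Two smaller objections are fair. An amendment needs sponsor and IRB approval (Section 16), so the cost is more than retyping. And the pregnancy-reporting window in Section 11.4.12 is not aligned with the label either: it runs to 120 days after completing the trial, or 30 days after stopping treatment if new anticancer therapy starts, whichever is earlier. For a woman who moves to new therapy, reporting could end 150 − 30 = 120 days before a 5-month contraception period does.

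**Conclusion.** The concern holds. For women of childbearing potential who receive atezolizumab, the minimum contraception commitment at entry is 94 to 97 days shorter than the minimum in the label. For those who stop at progression, no other protocol text makes up the difference. The gap itself rests only on stated durations and on atezolizumab being a study drug. The estimate of 0 to 2 women affected rests on the assumed 2% to 10%.

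This is a defect in the wording of the criteria, with a bearing on fetal safety and none on the statistical design. It should be corrected because the possible harm is serious and the correction is simple, even though few women are likely to be concerned.

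**What to change.** In inclusion 11, exclusion 7c and both Synopsis copies, require women of childbearing potential to use effective contraception throughout the study and until the later of:

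- (a) 8 weeks after the last study drug, whether MV-NIS or atezolizumab; and
- (b) at least 5 months after the last atezolizumab dose, if any was given.

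Part (a) keeps the present minimum for a woman who receives MV-NIS but no atezolizumab. The 8-week period for men can stay. Check that the consent form states the same period. It would be sensible in the same amendment to see whether the reporting window in Section 11.4.12 should cover the longer period.

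The cost is an amendment to two criteria and their copies with the usual IRB approval, a consent revision if the form differs, and a commitment about 3 months longer for the few women affected. Sample size, dose escalation and analysis do not change.
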